**Table: Hypothesized group means for negative mood for power calculations**

VACCINE RESPONSE (SD=7.7)			PLACEBO RESPONSE (SD=5.8)			
	Low Depression	High Depression		Low Depression	High Depression	
High Fitness	10	15.2	12.6	High Fitness	8.5	9.1
Low Fitness	11.2	25.2	18.2	Low Fitness	8.7	9.3
Average	10.6	20.2	15.4	Average	8.6	9.2

These means yield effect sizes for the vaccine response of  $d = 0.73$  for the average effect of fitness and  $d = 1.25$  for the average effect of depression. Importantly, in line with Hypothesis 3, they yield an effect size for depression of  $d = 1.8$  for women with low fitness and a smaller effect of  $d = 0.68$  for women with high fitness. Additionally, we will have baseline (pre-injection) measures of outcomes which will be used as covariates in models. In an ongoing study of breast cancer survivors, baseline negative mood was highly correlated with subsequent measures throughout the day, with  $r = 0.79-0.85$ . Inflammatory markers were similarly highly correlated, with correlations of  $r > 0.9$ . To be conservative in the power calculations we assume a single covariate with a correlation of  $r = 0.75$ . **Based on these hypothesized means and one covariate, a sample of size  $n = 180$  will give us 81% power to detect the three-way interaction effect of fitness by depression by injection type on mood. We will also have 94% power for the two-way interaction of depression by injection type and >99% power for the two-way interaction of fitness by injection type.** As previously noted, effects on IL-6 are expected to be larger and group differences should be as big or larger, thus this sample size should provide us the ability to detect the effects on IL-6 as well.

These calculations are conservative for several reasons. As previously noted, our sample is older than the sample on which we base our estimates, thus we will likely see even larger effects and more dramatic effects of age, depression, and fitness and should have higher power. Additionally, power calculations were made assuming fitness and depression were dichotomized; we will obtain continuous measurements of these covariates and thus expect higher power. We will also collect serial measurements of outcomes over time and thus expect to have higher power than if we only obtained a single post-injection measurement.

**Data Analysis Plan** Each subject will have two visits (vaccine, placebo), and within each visit the primary outcomes (inflammation, behavioral responses) will be measured before injection and then serially (every 90 minutes) over the subsequent ~7.5 hours. Primary data analyses will use area under the curve (AUC) to summarize within-visit inflammatory and behavioral responses for each outcome. Hierarchical linear regression models (HLMs) will then be used to capture within-subject correlation across the two visits. If significant effects are found, secondary analyses will use more complex multi-level HLMs to model the individual time points within visit in order to identify at what time in the post-injection period effects arise.

For Hypothesis 1, baseline relationships between cardiorespiratory fitness and inflammation and behavioral outcomes will be evaluated using HLMs; subjects will have two baseline measurements, one before each injection, so an HLM is needed to control for the within-subject correlation. Outcomes in these models will be baseline (pre-injection) inflammation, depressive symptoms, cognitive problems, pain, and fatigue, and predictors will include cardiorespiratory fitness and visit (first or second). Tests of the main effect of cardiorespiratory fitness will investigate baseline relationships between these variables. The effect of vaccine on these outcomes over time will also be investigated using HLMs. AUC for each outcome at each visit will be the dependent variable, and predictors will include injection type (vaccine/placebo), cardiorespiratory fitness, and their interaction, as well as the baseline (pre-injection) outcome level. Separate models will be fit for each of the primary outcome AUCs (inflammation, behavioral responses) and the effect of interest will be the two-way interaction of cardiorespiratory fitness by injection type (which is a between-subject\*within-subject interaction). This term will allow us to investigate differences in response for the vaccine compared to placebo (injection type effect) and how these differences differ by fitness level (cardiorespiratory fitness by injection type interaction).

For Hypothesis 2a, baseline relationships between inflammation and age as well as the effect of age on vaccine responses will be investigated using HLMs similar to those described for Hypothesis 1 with age

replacing cardiorespiratory fitness. For Hypothesis 2b similar HLMs will again be used, with depressive symptoms replacing cardiorespiratory fitness. For Hypothesis 2c, the HLMs with inflammation and behavioral AUC responses as outcomes will be modified by including both age and depression and their interaction as predictors. The test of the age by depression interaction will test whether the combination of older age and high depressive symptoms produces greater responses than the effect of either alone.

HLMs with AUC for inflammatory markers as well as behavioral responses as outcomes will also be used to test Hypothesis 3. Predictors will include injection type (vaccine/placebo), cardiorespiratory fitness, and age or depression, as well as all interactions and the baseline outcome level. Separate models will be used to test moderation of age and depression effects. To test whether cardiorespiratory fitness moderates the effect of age/depression on outcomes we will test the three-way interaction of injection type by age/depression by cardiorespiratory fitness. This is a three-way interaction, and we note that the primary interest is actually in the contrast testing the age/depression by cardiorespiratory fitness interaction for the vaccine injection. The post-placebo information serves to reduce error variance by allowing each woman to serve as her own control.

In all models we will control for BMI and insulin resistance to avoid possible confounding. Additionally, secondary analyses will control for use of aromatase inhibitors or tamoxifen; by including these variables as covariates, we will assess whether these medications impact cardiovascular (i.e., blood pressure, HRV) and inflammatory responses to the vaccine. Separately, we will assess whether tamoxifen or aromatase inhibitor use is related to cardiovascular variables and inflammation at baseline.

In secondary analyses, we will also assess antidepressant use as a possible confounder and control for this in analyses. We note again that the crossover design allows each woman to serve as her own control, thus mitigating the effect of possible confounders.

The analyses described above involve a number of tests of hypotheses and primarily focus on complex interactions. We recognize the importance of ensuring such tests have adequate statistical power for detection of effects as well as controlling, to the extent possible, the frequency of Type I errors. To control Type I error rates and minimize their impact, when appropriate, multivariate analysis of variance (MANOVA) will be used and/or alpha rates will be adjusted within subsets of hypotheses so as to control Type I error rates across sets of hypotheses tests. In addition, emphasis will be given to estimates of effect size so that findings that are statistically significant but of little practical relevance will not receive great attention.

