The three specific aims for the proposed study are to evaluate (1) the effect of cardiorespiratory fitness on vaccine response, (2) the effect of age and depressive symptoms on vaccine response, and (3) the moderating effect of fitness on the age- and depression-related effects on vaccine response. Since each woman will serve as her own control by receiving both the vaccine and the placebo injection, the corresponding hypotheses all involve complex interactions: (1) the two-way interaction between fitness and injection type (vaccine/placebo), (2) the two-way interaction between age/depression and injection type, and (3) the three-way interaction of fitness by age/depression by injection type. Sample size requirements are considerably higher for testing higher-order interaction terms, thus we based required sample size on the tests of the third specific aim: the three-way interaction between fitness, age/depression, and injection type, while ensuring adequate power for the first two aims as well. Throughout we assumed 2-tailed tests with an 0.05 level of significance and used SAS PROC GLMPOWER for calculations.

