Data from Wright [56] gives us an estimate of the overall (averaged across fitness and age/depression) effect of vaccine and placebo on negative mood: at 3h post-injection the mean in their study was 12.8 (SD=7.7) for vaccine and 7.4 (SD=5.8). We anticipate larger effects in our sample as we are recruiting older subjects who are breast cancer survivors, thus we assume that average negative mood responses to both the vaccine and placebo will be 20% higher in our sample of older breast cancer survivors. In order to calculate required sample size for the three-way interaction, we hypothesized the mean negative mood post-vaccine and also post-placebo for each of four groups: (a) high fitness/low depression, (b) high fitness/high depression, (c) low fitness/low depression, (d) low fitness/high depression. We hypothesized that the highest negative mood post-injection (either type) would be in group (d) low fitness/high depression, and the lowest negative mood would be in group (a) high fitness/low depression. Additionally we hypothesized that the average effect of depression on mood would be larger than the effect of fitness on mood and (as in Hypothesis 3) the effect of depression among women with high fitness would be smaller than the effect of depression among women with low fitness. The hypothesized means are shown in the **Table** below. We note that even the largest hypothesized mean is only approximately 1.25 SD above the estimated overall mean and the smallest is only  $\frac{3}{4}$  SD below this mean, thus these estimates seem reasonable.

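### The power statement exchanges the two two-way interaction powers, and its 81% three-way power is lower than the stated crossover inputs give

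*Combined protocol and SAP*

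**What the plan says.** Under Power and Sample Size in section G, the sample size rests on the three-way interaction of fitness, age or depression, and injection type. The worked case is depression, with negative mood as the outcome. The method is described as follows: "Throughout we assumed 2-tailed tests with an 0.05 level of significance and used SAS PROC GLMPOWER for calculations". The design is described as a within-woman comparison: "Since each woman will serve as her own control by receiving both the vaccine and the placebo injection". The text also says that "the average effect of depression on mood would be larger than the effect of fitness on mood".

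The table of hypothesized group means gives eight cell means, with SD 7.7 after vaccine and 5.8 after placebo. The text below it reports vaccine-visit effect sizes of 0.73 for fitness and 1.25 for depression, and assumes one covariate with correlation 0.75. It concludes that 180 women "will give us 81% power to detect the three-way interaction effect of fitness by depression by injection type on mood". It then says: "We will also have 94% power for the two-way interaction of depression by injection type and >99% power for the two-way interaction of fitness" (again with injection type).

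The Data Analysis Plan uses hierarchical models that "will then be used to capture within-subject correlation across the two visits". On the three-way test it adds: "The post-placebo information serves to reduce error variance by allowing each woman to serve as her own control".

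**The concern.** The order of the two-way powers contradicts the means they are said to come from. Depression is given the larger effect throughout, yet its interaction is reported as the harder one to detect. A reader would take the Aim 2 depression test to be weaker than the Aim 1 fitness test, when the plan's own assumptions make it the stronger.

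The 81% is the figure that justifies n = 180. It appears beside a crossover description, two SDs and a strong covariate, but it is too low to follow from them. No between-visit correlation is given anywhere, so a reader cannot tell what calculation was run.

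**Working it through.** **Inputs** (Power and Sample Size and its table): N = 180 women; two-sided alpha 0.05; SD 7.7 (vaccine) and 5.8 (placebo); covariate correlation r = 0.75; one post-injection value per visit. Equal group sizes are assumed; the printed margins are unweighted averages of the cells. The between-visit correlation ρ is not stated, so it is varied.

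**Contrasts.** Vaccine minus placebo in each cell:

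- high fitness, low depression: 10 − 8.5 = 1.5
- high fitness, high depression: 15.2 − 9.1 = 6.1
- low fitness, low depression: 11.2 − 8.7 = 2.5
- low fitness, high depression: 25.2 − 9.3 = 15.9

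From these:

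- Depression by injection: (6.1 + 15.9)/2 − (1.5 + 2.5)/2 = 11.0 − 2.0 = 9.0
- Fitness by injection: (2.5 + 15.9)/2 − (1.5 + 6.1)/2 = 9.2 − 3.8 = 5.4
- Three-way: (15.9 − 2.5) − (6.1 − 1.5) = 13.4 − 4.6 = 8.8

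**Order of the powers.** In the three-factor model both two-way contrasts have the same standard error, and the three-way contrast has twice that. In units of the two-way standard error the contrasts stand as 9.0 (depression), 5.4 (fitness) and 8.8/2 = 4.4 (three-way). The powers must follow that order whatever N, SD, r or ρ may be.

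**What the 81% implies.** A 1-df F test with 81% power needs a noncentrality of about 8.14 (error df 176; hardly different at 167).

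- Fitness: 8.14 × (5.4/4.4)² = 12.26, power 93.6%
- Depression: 8.14 × (9.0/4.4)² = 34.1, power above 99.9%

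If 94% did belong to depression (noncentrality about 12.49):

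- Fitness: 12.49 × (5.4/9.0)² = 4.50, power 56%
- Three-way: 12.49 × (4.4/9.0)² = 2.99, power 40%

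So the three printed figures cannot all be right as labelled. With the two labels exchanged they agree.

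**Reproducing the printed values.** Treat the eight cells as independent, with N observations in total, SD 7.7 throughout and r = 0.75. The residual variance is 7.7² × (1 − 0.75²) = 25.94. The variance of a two-way contrast is 16 × 25.94/N, and of the three-way contrast 64 × 25.94/N.

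| N | Three-way | Fitness | Depression |
|---|---|---|---|
| 176 | 81.3% | 93.8% | >99.9% |
| 180 | 82.2% | 94.3% | >99.9% |

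This is consistent with the printed numbers but is not proof of their source. A paired calculation with SD 7.7 at both visits, ρ = 0.10 and no covariate matches as well. Neither uses all the stated inputs, and both put 94% on fitness.

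**The crossover with the stated inputs.** The variance of the within-woman difference is Vd = (1 − r²)(7.7² + 5.8² − 2ρ × 7.7 × 5.8). The variance of a two-way contrast is 4Vd/180, and of the three-way contrast 16Vd/180. For r = 0.75 and ρ = 0, Vd = 0.4375 × 92.93 = 40.66. The three-way noncentrality is then 8.8²/(16 × 40.66/180) = 21.4, and the power 99.6%. The rows with r = 0 show the case where the covariate removes none of the variance of the difference.

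| Covariate | ρ | Three-way | Fitness | Depression |
|---|---|---|---|---|
| r = 0.75 | 0 | 99.6% | >99.9% | >99.9% |
| r = 0.75 | 0.25 | >99.9% | >99.9% | >99.9% |
| r = 0.75 | 0.5 | >99.9% | >99.9% | >99.9% |
| r = 0 | 0 | 86.1% | 96.2% | >99.9% |
| r = 0 | 0.25 | 93.7% | 99.0% | >99.9% |
| r = 0 | 0.5 | 98.8% | 99.9% | >99.9% |

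A simulation of 4,000 runs agrees: three-way 86.3%, 94.2% and 98.9% in the r = 0 rows, and 99.5% at r = 0.75, ρ = 0. With both printed SDs and no covariate benefit, ρ would have to be about −0.16 to bring three-way power down to 81%.

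**The case against.** The label exchange has no good answer: no other part of the plan repairs it, and the printed margins rule out unequal groups as an explanation. The effect sizes 0.73 and 1.25 are vaccine-visit effects rather than interaction contrasts, so they support the order without proving it. The proof is the 9.0 against 5.4.

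The case against the second part is stronger. The 81% is not a slip of arithmetic, since an independent-cells calculation gives it. The crossover power cannot be computed without a correlation that the plan omits. One paired variant even falls below 81%: SD 7.7 at both visits, no covariate and ρ = 0 gives 76.9%. The plan already calls its calculation conservative, and nothing about enrolment turns on the point. All of this is true, but it leaves the point standing. The 76.9% variant drops two stated inputs. The plan's reasons for calling itself conservative (older sample, dichotomized predictors, one post-injection value) do not include ignoring the pairing. With the inputs it does state, no non-negative correlation gives 81%.

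One caution stands in full. The 94% for fitness belongs to the model that also contains depression. The Data Analysis Plan tests Aim 1 without depression, so the depression spread enters the residual. If baseline absorbs none of that spread, the eight-cell calculation then gives 80–81% for fitness. The paired calculation with both SDs and ρ = 0 gives 91% without the covariate and 99.3% with r = 0.75. Depression stays above 99.9% in the corresponding single-factor calculations, so the order is unaffected.

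**Conclusion.** Both parts hold. The exchange of labels is certain: it follows from the printed means and the equal standard errors in the three-factor model, and needs no assumption about N, SD, covariate or correlation. Read correctly, the plan's own calculation gives about 94% for fitness by injection and above 99% for depression by injection.

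The 81% is lower than the stated crossover inputs give. Three-way power is at least 99.6% for ρ of 0 or more with r = 0.75, and 86.1% to 98.8% over ρ = 0 to 0.5 if the covariate does nothing. These figures assume equal groups, a single post-injection value and the table's means. How the 81% was obtained is not established.

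The three-way error is conservative. It does not show that n = 180 is too small or that Aim 1 is underpowered. What needs correcting is a headline power statement that misorders two aims and whose basis is not documented.

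**What to change.** At the least, if the present calculation is kept, exchange the labels: 94% for fitness by injection type and above 99% for depression by injection type. Say that these apply to the model containing fitness, depression and injection type, and state the design structure and SD used.

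Preferably, recompute all three powers on the within-woman vaccine-minus-placebo difference in the four fitness-by-depression groups, with both SDs and the r = 0.75 covariate. State the between-visit correlation assumed, for example results at 0, 0.25 and 0.5, and whether the covariate is measured separately at each visit.

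The cost is a change of protocol wording and one re-run of the power program. Enrolment does not change.

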### OBJECTIVES

**Specific Aim 1:** To evaluate the relationships between cardiorespiratory fitness and inflammatory and behavioral responses (negative mood, fatigue, pain, and cognitive problems) to typhoid vaccine. **Hypothesis 1:** Prior to the vaccine or placebo, better cardiorespiratory fitness will be associated with lower levels of inflammation, depressive symptoms, fatigue, pain, and cognitive problems. The vaccine will produce larger inflammatory responses and greater negative behavioral changes than the placebo. Better cardiorespiratory fitness will attenuate the magnitude and duration of both proinflammatory and behavioral responses to the vaccine.

**Specific Aim 2:** To determine the effects of age and depressive symptoms on inflammatory and behavioral responses to typhoid vaccine and placebo. **Hypothesis 2a:** Compared to younger women, older women will have higher levels of inflammation prior to vaccine or placebo. Aging will amplify the inflammatory and behavioral responses to typhoid vaccine, with older women showing more enhanced and prolonged responses than younger women. **Hypothesis 2b:** Prior to the vaccine or placebo, women with higher levels of depressive symptoms will have higher levels of inflammation than less depressed women, as well as higher levels of fatigue. Depressive symptoms will intensify vaccine responses, such that women who are more depressed will produce larger and longer-lasting proinflammatory and behavioral responses to the vaccine than women who are less depressed. **Hypothesis 2c:** The combination of older age and high depressive symptoms will produce greater and longer-lasting increases in inflammation and negative behavioral responses to typhoid vaccine than either alone.

**Specific Aim 3:** To assess the ability of cardiorespiratory fitness to moderate age- and depression-related responses to typhoid vaccine. **Hypothesis 3:** Women with better cardiorespiratory fitness will show smaller age- and depression-related inflammatory and behavioral responses to typhoid vaccine.

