**Objective Cognitive Assessments:** We will measure aspects of cognitive functioning that have been responsive to endotoxin administration and chemotherapy exposure as suggested by other studies and our neuropsychology consultant, [name] PhD, including verbal memory, reaction time, attention, and executive function [79, 265-270]. At each visit, we will include both baseline and post-injection assessments. Unless otherwise noted, assessment tasks will be completed at baseline, 3 hours, and 4.5 hours post-injection, to coincide with expected peak inflammatory responses and prior studies [79, 267, 271]. The order in which tasks are administered will remain the same across subjects and conditions. Alternate versions of the tests will be administered to avoid practice effects, and test versions will be counter-balanced. The **Hopkins Verbal Learning Task** will assess verbal learning and short- and long-term verbal memory [266, 272]. Subjects are asked to immediately recall a presented word list, then to recall it after a 20-minute delay. The **Conners' Continuous Performance Test** is widely used to measure attention, concentration, and reaction time [273]. On this computerized task, subjects are instructed to press the space bar when a target stimulus appears, but to not press it when any other stimulus appears. To reduce participant burden, we will only administer this task at baseline and 3hr post-injection. The **Stroop Task** will be used to measure executive function. The Stroop requires participants to name a color of a word while inhibiting the natural inclination to read the actual word itself [274]. Significant practice effects exist with the Stroop Task [275], so participants will only be tested at 3h post-injection at both visits, consistent with other studies [265]. For the emotional Stroop, participants name the color in which negative or threatening words are printed, rather than reading the word itself [276]. Following work by Mogg et al. [277] we will use words from their lists from each of the following categories: depression words (desolate, discouraged, dismal, forsaken, glum, grief, mournful, suicide, tearful, tormented, blame, despair, desperate, drained, forlorn, helpless, hopeless, listless, pessimistic, sorrow), neutral (uncategorized) words (adjacent, amount, assembled, bearings, bent, bilateral, boulder, casement, celery, circuit, alignment, angle, border, boundary, bowl, branched, brochures, capacity, contents, density), and negative words (anxiety, assassin, assault, betrayal, brutal, chaotic, crisis, dangerous, death, destruction, ambulance, atrocious, brutal, devil, hazardous, horrible, hostile, hurricane, maniac, menacing). The word types were matched for length and frequency based on published norms [278]. The words will be presented in random order. The depression and negative word interference scores for each subject and assessment time point will be calculated by subtracting the mean latency for the neutral words from those for depression-related words, and the same procedure will be used for negative words [277]. Thus, larger values indicate slower responses to emotion-relevant words than neutral household words [277].

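### Visit (first or second) is in the baseline models but in none of the AUC models; add it, and report the H2b baseline test without post-vaccine baselines as a sensitivity analysis

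*Combined protocol and SAP*

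**What the plan says.** The study is a balanced two-sequence crossover with sessions 10-30 days apart (section C, Study Design). Section G, Data Analysis Plan, describes two families of models.

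- **Baseline models.** The plan notes that "subjects will have two baseline measurements, one before each injection, so an HLM is needed", and "predictors will include cardiorespiratory fitness and visit (first or second").
- **AUC models.** For Hypothesis 1, "predictors will include injection type (vaccine/placebo), cardiorespiratory fitness, and their interaction, as well as the baseline (pre-injection) outcome level". Hypotheses 2a to 2c reuse or extend this form. For 2b, "For Hypothesis 2b similar HLMs will again be used, with depressive symptoms replacing cardiorespiratory fitness". The list for Hypothesis 3 has injection type, fitness, age or depression, all their interactions and the baseline outcome. None of these lists has visit or sequence.
- **Added to everything.** "In all models we will control for BMI and insulin resistance to avoid possible confounding". Visit is not among these additions.

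On the role of the placebo session, the plan says: "The post-placebo information serves to reduce error variance by allowing each woman to serve as her own control". Section D (Objective Cognitive Assessments) says: "Significant practice effects exist with the Stroop Task [275], so participants will only be tested at 3h post-injection at both visits". The baseline part of Hypothesis 2b reads: "Prior to the vaccine or placebo, women with higher levels of depressive symptoms will have higher levels of inflammation".

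**The concern.** In a two-period crossover, a general difference between the first and second session (familiarity with the unit, practice, anticipation) enters every within-woman difference with a sign that depends on sequence. The random subject effect handles correlation between visits; it does not remove this shift. The plan uses the term where it tests baseline associations and leaves it out where it tests the injection-type interactions of Aims 1 to 3. What is at stake is precision, which is the stated reason for using the placebo session.

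The point is clearest for an outcome measured once per visit with no same-day baseline. The Stroop is one, and the plan itself names practice effects for it.

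A second, smaller matter concerns the baseline test of Hypothesis 2b. It pools both baselines, so some come after the study vaccine. Visit shifts all second baselines equally and cannot tell those after vaccine from those after placebo.

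**Working it through.** **Plan's own power figure.** Inputs from section G, Power and Sample Size: SD 7.7, covariate correlation 0.75, n = 180, two-sided 0.05. Three-way contrast = (25.2 - 11.2) - (15.2 - 10) - [(9.3 - 8.7) - (9.1 - 8.5)] = 8.8. With eight independent cells of 22.5 and error variance 7.7² × (1 - 0.75²) = 25.94, power is 82.2%; with cells of 22 (176 in total) it is 81.3%. The stated 81% reproduces. That calculation contains neither within-woman differences nor a visit effect, so the effect of visit has to be worked on the within-woman scale.

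**Visit left out of the AUC models (mood).** Assumptions: the plan's 3-hour SDs stand in for AUC SDs; the visit shift is 3 points; the residual correlation between visits, ρ, is 0 to 0.5; the baseline slope equals the covariate correlation; there are four groups of 45 women.

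- Residual SDs: 7.7 × √(1 - 0.75²) = 5.09 and 5.8 × √(1 - 0.75²) = 3.84.
- SD of the difference: √(5.09² + 3.84² - 2ρ × 5.09 × 3.84) = 6.38 (ρ = 0) or 4.60 (ρ = 0.5).
- Variance inflation from omitting visit: residual shift² / SD².

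| Shift | Residual shift | ρ = 0 | ρ = 0.5 |
|---|---|---|---|
| Shared with baseline, r = 0.75 | 3 × 0.25 = 0.75 | +1.4% | +2.7% |
| Shared, r = 0.79 | 0.63 | +1.1% | +2.2% |
| Shared, r = 0.85 | 0.45 | +0.8% | +1.5% |
| Wholly post-injection | 3 | +22% | +43% |

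Power for the 8.8 contrast, with SE = SD × √(4/45) and 176 df, is 99.6% at ρ = 0 with no shift. In the wholly post-injection case it is 98.6% at ρ = 0 and 99.96% at ρ = 0.5.

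**Stroop.** With no baseline, inflation = d² / (2(1 - ρ)), where d is the practice gain in SDs. The documents give neither d nor ρ. Assuming d = 0.2 to 0.5 and ρ = 0.5 to 0.8, the variance rises from 0.04/1.0 = 4% to 0.25/0.4 = 62%, and the SE by 2% to 27%.

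**Cost of the visit term.** One degree of freedom in about 180: 1/180 ≈ 0.6% of variance.

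**Baselines after vaccine.** 180 × 2 = 360 baselines. With 1:1 sequences and no dropout, 180/2 = 90 follow the study vaccine, a quarter of the total.

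**Size of a possible H2b carryover.** The only basis in the documents is the influenza study in section A.7.a: F(1,116) = 7.42, so r = √(7.42/123.42) = 0.245. Suppose the full effect occurred in all 90 women, with test-retest correlation ρ between baselines:

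- Carryover per SD of depression: c = r/√(1 - r²) × √(2(1 - ρ)) = 0.113 SD at ρ = 0.9.
- Shift in the pooled slope: c/4 = 0.028 SD.
- SE: √(((1 + ρ)/2)/180) = 0.0726.
- Rejection of a true null: 6.75%, or 5.4% at half the carryover.
- At ρ = 0.7 and 0.5 the full-size figures are 11.0% and 16.5%.

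The only correlation given for inflammatory markers is above 0.9, between measures within a day.

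**Precision of the sensitivity analyses.** Information in the pooled analysis is 180/((1 + ρ)/2). Without post-vaccine baselines (270 values) it is 90 + 90/((1 + ρ)/2), so the SE rises by 1.3% at ρ = 0.9 and 6.9% at ρ = 0.5. With first-visit baselines only (180 values), the SE ratio is √(2/(1 + ρ)), a rise of 2.6% and 15.5%.

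**The case against.** **Little is lost on the primary outcomes.** This stands. Without carryover the interactions are unbiased when sequences are balanced, and a shift shared with baseline adds at most about 3% to the variance. The 22% to 43% figures need a 3-point shift that is absent from the same-day baseline. That is 56% of the vaccine-placebo difference in the study used for power (12.8 - 7.4 = 5.4), and nothing in the documents suggests it.

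**The predictor lists are not exhaustive.** True: BMI and insulin resistance are added afterwards. But visit is named for one family of models and not for the other, so an analyst following the text would leave it out.

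**The Stroop is secondary, has no AUC, and has safeguards.** Cognition is a secondary outcome and no Stroop model is written down. Section D also provides for alternate, counterbalanced test versions. These may reduce a second-visit gain but need not remove it, so the advice to include visit stands; the 4% to 62% range remains illustrative.

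**All 360 baselines may fit Hypothesis 2b as worded.** Each woman receives both injections, so the hypothesis can be read as before that visit's injection. A reader might infer that a quarter of the values contradict the hypothesis and that the primary baseline tests must be replaced. The documents do not support that. The carryover evidence is for another vaccine, in adults of mean age 71, with no unvaccinated comparison described. Against it, section E calls the typhoid response transient, section A.2 puts peaks at hours, and section B says prior typhoid exposure is not reliably associated with responses. No carryover evidence is offered for fitness or age.

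**Conclusion.** The omission is real and worth correcting, mainly because correction is almost free. On mood the expected gain is small: about 1% to 3% of variance for a 3-point shift shared with baseline. In the worst case considered, three-way power falls only from 99.6% to 98.6%. These figures rest on an assumed shift, 3-hour SDs used for AUC, and assumed residual correlations. The gain could be larger for once-per-visit outcomes, but the documents give no practice effect size.

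Two stronger conclusions might be drawn and should not be. The first is that leaving out visit biases the interaction tests; with balanced sequences and no carryover it does not. The second is that the H2b baseline result is materially contaminated. The count of about 90 in 360 is right under 1:1 allocation and no dropout, but carryover is possible rather than shown. Even at full influenza size it lifts the false-positive rate only to about 6.75% at an assumed correlation of 0.9. The 11% to 16.5% figures need lower correlations, which the documents do not give. This justifies a sensitivity analysis, not a different primary test.

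**What to change.** 1. Add visit (first or second) as a fixed effect to every AUC model for Hypotheses 1 to 3, and to the model for any outcome measured once per visit, such as the Stroop. Cost: one degree of freedom.
2. Keep the pooled two-baseline model, with visit, as the primary analysis of the baseline hypotheses. For the H2b baseline test, prespecify a sensitivity analysis that either drops the second-visit baselines of vaccine-first women (270 values) or uses first-visit baselines only. The cost in SE falls on the sensitivity analysis alone.
3. Do not let a carryover test decide which baselines to use. Its power is about 39% even against the full influenza-size effect (z = 0.2529/√(2/90) = 1.70).

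All three are changes to analysis-plan wording. No visit, sample or procedure changes.
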